12.3 Additional analyses

The survival analyses (OS, RFS, EFS) will be repeated using a different censoring approach than presented in 12.2. The calculation will be otherwise similar as previously presented, except for patients receiving a stem cell transplant (SCT). For these patients, the patient is censored at the time of the SCT.

13 Analysis of safety

All subjects who have participated in the study will be included in the safety analysis.

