No standard regimen exists for the treatment of patients with relapsed acute myeloid leukemia (AML), particularly in patients with a first remission duration of less than 1 year ⁽¹⁶⁾. A number of agents have activity in recurrent/relapsed with an overall response rate of 20-80%, depending on study design and treatment (see Table 1, Appendix 1). Re-induction with Ara-C and daunorubicin will result in a 50% CR rate in patients who had a first remission lasting longer than 1 year ⁽¹⁷⁻¹⁹⁾. In a trial of mitoxantrone in combination with Ara-C in patients with refractory or relapsed AML with 49 patients 62.5% with first relapse AML achieved complete remission while none of the four patients with more than one prior remission responded ⁽²⁰⁾. A triple combination of mitoxantrone, etoposide, and cytarabine (MEC) demonstrated a CR induction rate of 55% in a population including 30 patients with relapsed AML, 28 patients with primary refractory AML, and 16 patients with secondary AML ⁽²¹⁾. A phase 1-2 study of clofarabine plus Ara-C in 25 patients with relapsed acute myeloid leukemia 7 (22%) achieved complete remission (CR), and 5 (16%) achieved CR with incomplete platelet recovery (CRI), for an overall response rate of 38% ⁽²²⁾. For patients not achieving a complete remission the only potentially curative treatment option is allogeneic transplantation with up to 20% of patients being long term survivors ⁽¹⁴⁾.

Therefore, the combination of Ara-C and idarubicin was chosen for standard induction therapy and if the patient receives complete remission transplantation is recommended.

In the light of a dismal prognosis for patients with relapsed/refractory AML a great clinical need exists for new treatment options.

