3.1.2 Definition of Treatment Cycle

All enrolled patients will be treated with cytosine arabinoside (Ara-C) at a dose of 100 mg/m² continuous infusion (day 1-7) and idarubicin at a dose of 10 mg/m² i.v. (days 1,3,5) every 4 weeks and Selinexor for a maximum of 2 cycles. During the second cycle the idarubicin dose is restricted to 2 administrations on day 1 and 3.

[figure not shown]
Patients will receive oral Selinexor 60 mg twice weekly in weeks 1-3 of a 4-week cycle (Monday/ Wednesday or Tuesday/ Thursday or Wednesday/Friday) starting on day 2 of week 1 (total of 6 doses per induction cycle).

If a CR or CRi was achieved, patients will be recommended for stem cell transplantation. If a PR is achieved patients can undergo a second, identical treatment cycle.

In patients who are not eligible or do not undergo additional stem cell transplantation, but, in the opinion of the investigator, are benefiting from Selinexor, then oral Selinexor dosed twice weekly in weeks 1-3 of a 4-week cycle may be continued parallel to 3 cycles of consolidation therapy with Ara-C until relapse or toxicity develops. The dose of Ara-C is 3 g/m² IV for 2h every 12 hours at 3 consecutive days for patients with good performance status and younger than 60 years (in total 6 doses). If patients are older than 60 years the dose is 1 g/m² IV for 2h every 12 hours at 3 consecutive days. During consolidation Selinexor dosing (60 mg) will start on day 2 of week 1 of a 4-week cycle and will be continued twice weekly during weeks 1-3 of a 4-week cycle (total of 6 doses per cycle). Selinexor twice weekly (Monday/ Wednesday or Tuesday/ Thursday or Wednesday/Friday) in weeks 1-3 at a dose of 60 mg (total of 6 doses per 4-week cycle) may continue until relapse or for maximally 1 year of treatment.

Patients achieving a > 50% blast reduction after the end of 2 induction cycles and in the opinion of the investigator, are benefiting from Selinexor and are not candidates for Stem cell transplantation, oral Selinexor dosed twice weekly in weeks 1-3 may be continued. Drug administration will occur twice weekly, on days 1 and 3 of weeks 1-3 of a 4-week cycle at a dose of 60 mg (e.g. on Monday and Wednesday or on Tuesday and Thursday or on Wednesday and Friday). One cycle is 4 weeks with 6 doses of Selinexor.

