3.1.3 Treatment Duration

Treatment duration for patients achieving CR or CRI during induction will be 1 or 2 cycles of 4 weeks each. These patients will be recommended for stem cell transplantation and have their end of treatment prior to SCT and will be followed for event-free and overall survival.

For patients achieving CR or CRI but who are not eligible or do not undergo additional stem cell transplantation, will continue in consolidation/maintenance therapy with 3 cycle of AraC combined with 4-week cycles with twice-weekly Selinexor during weeks 1 and 3 until relapse (for maximally 1 year of treatment).

Patients with a > 50% blast reduction at the end of 2 induction cycles and in the opinion of the investigator, are benefiting from Selinexor, will in maintenance therapy with 4-week cycles with twice-weekly Selinexor in weeks 1-3 until progression of disease (for maximally 1 year of treatment).

For patients for whom none of the above mentioned is achieved after 2 4-week induction cycles will discontinue study and will be followed for overall survival.

In any case, treatment will be discontinued upon progression of disease (PD) or unacceptable toxicity, withdrawal of consent by the patients, or non-compliance by the patient with protocol requirements.

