5.3 Planned Treatment of the Patient after End of Treatment Phase

After completion of the study at routine follow-up (EOT), patients will generally be treated at the discretion of the investigator according to medical routine, although stem cell transplantation is recommended if a donor is available and no contra-indications exist.

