12.2 Secondary efficacy variables

The secondary efficacy variables; rate of partial remissions, percentage of patients being transplanted after induction therapy and early death rate will be analysed using similar methods as with the primary analysis.

Overall survival, recurrence-free-survival and event-free survival will be analysed applying the Kaplan-Meier-method (KM). OS is calculated from the date of informed consent to the date of death, the patients still alive will be censored at the last date of follow-up. RFS is calculated from the date of informed consent to the date of recurrence or death, whichever occurs first, censoring patients who were alive without recurrence on the date of last follow-up visit. EFS is calculated from the date of CR/CRi until death or relapse, whichever occurs first. Patients are censored on the date of last follow-up visit if they are alive without relapse.

The survival curves will be displayed graphically for the overall population and by dosage schedule. In addition median survival and follow-up times (including interquartile range and 95 % CI if feasible) will be calculated.

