14.2 Efficacy data

Figure 14.2.1 Kaplan-Meier curves for Overall survival (ITT)

Figure 14.2.2 Kaplan-Meier curves for Recurrence-free survival (ITT)

Figure 14.2.3 Kaplan-Meier curves for Event-free survival (ITT)

Figure 14.2.4 Kaplan-Meier curves for Overall survival (censoring at time of SCT) (ITT)

Figure 14.2.5 Kaplan-Meier curves for Recurrence-free survival (censoring at time of SCT) (ITT)

Figure 14.2.6 Kaplan-Meier curves for Event-free survival (censoring at time of SCT) (ITT)

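### Censoring overall survival at transplant (SAP 12.3) is informative because transplant follows response, and it is likely to understate survival; the same holds for RFS only if non-responders are included, and for EFS the direction is unknown

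*SAP*

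**What the plan says.** SAP 12.2 holds the main survival analyses. For OS, "OS is calculated from the date of informed consent to the date of death", and "the patients still alive will be censored at the last date of follow-up"; patients are thus followed through SCT, and responders and non-responders share one curve. RFS also starts at consent and ends at recurrence or death; the SAP does not say whether patients who never respond are included. EFS in the SAP starts at the date of CR/CRi. The protocol (8.4.3) instead counts failure to reach CR/CRi as an EFS event.

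SAP 12.3 repeats all three with a different rule for transplanted patients: "For these patients, the patient is censored at the time of the SCT". The table and figure plan (SAP 19.2) gives these analyses three figures (14.2.4 to 14.2.6) and three tables (14.2.3.1 to 14.2.3.3).

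On who is transplanted, protocol 3.1.2 says: "If a CR or CRi was achieved, patients will be recommended for stem cell transplantation". Protocol 3.1.3 adds, for patients in CR or CRi after one or two induction cycles: "These patients will be recommended for stem cell transplantation and have their end of treatment prior to SCT". SCT is not confined to responders. Protocol 5.3 says that after end of treatment "stem cell transplantation is recommended if a donor is available and no contra-indications exist", and protocol 1.1.1 says: "For patients not achieving a complete remission the only potentially curative treatment option is allogeneic transplantation".

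Neither the SAP nor its 2018 addendum states an independent-censoring assumption for the 12.3 curves, adjusts for response, or says how the curves should be read.

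**The concern.** Kaplan-Meier treats a censored patient as having the same future risk as those who remain in the risk set. In the OS analysis, a patient becomes a candidate for censoring largely by reaching CR or CRi. If responders live longer than non-responders, censoring at SCT removes longer-lived patients and leaves a risk set richer in non-responders. The curve then falls too fast, whatever SCT itself does.

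The SAP gives no purpose for 12.3, but a reader will probably take the curves as survival without the contribution of SCT. For OS they show neither observed survival nor survival had SCT been withheld.

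The curves may also be compared between dosing schedules, because 12.2 displays survival by schedule and 12.3 otherwise follows it. The bias depends on the response rate, so a contrast between schedules could be distorted as well as the level.

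**Working it through.** The documents give no survival by response, no share transplanted and no figure for the censored curves, so there is no plan figure to reproduce. The sizes below are illustrations with SCT given **no effect** on any hazard.

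**OS, main illustration.** All inputs are assumed: response 50% (the protocol's hypotheses in 8.1 span 30% to 60%); exponential survival with medians 12 months (responders) and 4 months (non-responders); 75% of responders alive at 2 months and no non-responders transplanted then.

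1. True 12-month OS: 0.5 × 0.5^(12/12) + 0.5 × 0.5^(12/4) = 0.25 + 0.0625 = 0.3125.
2. Survival to 2 months: 0.5 × 0.5^(2/12) + 0.5 × 0.5^(2/4) = 0.4454 + 0.3536 = 0.799.
3. Risk set just after censoring: 0.25 × 0.4454 + 0.3536 = 0.465. Responders are now 0.111/0.465 = 24% of it, against 0.4454/0.799 = 56% just before.
4. Of that risk set, alive at 12 months: 0.25 × 0.25 + 0.0625 = 0.125.
5. SCT-censored Kaplan-Meier at 12 months: 0.799 × 0.125/0.465 = 0.215.
6. Gap: 31.2% − 21.5% = 9.8 points (before rounding).

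**Varying the inputs, same model, 12-month OS.**

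| Responders transplanted | Non-responders transplanted | Gap (points) |
|---|---|---|
| 75% | 0% | 9.8 |
| 75% | 30% | 7.6 |
| 50% | 0% | 5.3 |
| 50% | 30% | 2.6 |
| 75% | 75% | 0 |

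With no non-responders transplanted, 50% to 90% of responders transplanted, and median pairs 10/6, 12/4 and 15/3 months, the gap runs from 2.6 to 19.0 points at 50% response, and from 2.0 to 21.5 points over 30% to 60% response. A separate simulation (transplant at 2 to 4 months, 50% to 80% of responders and no non-responders, medians 12/4, 18/4 and 24/6, response 30% to 60%) gives 3.7 to 14.4 points. The bias is also zero if response is not prognostic.

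**Between schedules.** With the main inputs but response 30% and 60%, true 12-month OS is 23.8% and 35.0%, a difference of 11.3 points before rounding. The censored curves give 17.0% and 24.5%, a difference of 7.6.

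**RFS.** If all patients are included (45% response, half of responders transplanted), the 12-month change from censoring depends on the assumed medians, written as responder relapse-or-death/non-responder death: −4.6 points for 12/4, −1.2 for 8/6, 0 for 6/6, +1.2 for 6/8. If RFS is restricted to responders, this mechanism is absent.

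**EFS as the SAP defines it.** Everyone analysed is already a responder. With an assumed median of 10 months, SCT 1 to 3 months after CR and 50% to 80% transplanted, the 12-month change depends on the hazard of SCT-bound responders relative to the others: 0 at a ratio of 1, −5.2 to −15.0 points at ratios 0.7 to 0.5, and +5.9 to +14.3 points at 1.5 to 2.0. Under the protocol's definition, with non-response counted at 2 months, the change is 0 to about −1 point.

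**Which alternatives avoid the problem for OS.** The no-SCT curve in a Simon-Makuch plot removes each patient at SCT, so it is the same estimate as the SCT-censored Kaplan-Meier curve. In the main illustration, an unadjusted Cox model with SCT as a time-dependent covariate returns a hazard ratio of about 0.5 although the true value is 1. With response also in the model it returns about 1.0.

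**The case against.** The strongest reply is that the SAP already handles this sensibly. The 12.3 analyses are headed as additional, the uncensored curves in 12.2 are the planned secondary analysis, both sets are separately labelled, and no test or decision uses the censored curves. All of that stands, and it is why the point is minor.

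A second reply is that SCT is only recommended, that the protocol provides consolidation and maintenance for responders who are not transplanted, and that non-responders may be transplanted too. This also stands. It reduces the OS bias, and removes it if rates are equal, but the protocol ties the recommendation during the study to CR/CRi, so equal rates would be surprising.

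A reader might infer that all three sets of censored curves understate survival. The documents do not support that. The SAP's EFS risk set contains no non-responders, so it cannot become enriched for them. Selection among responders could work either way: fitness and donor availability might favour transplanted patients, while protocol 1.1.1 describes, for first remission, intermediate- and unfavourable-risk patients as those transplanted. For RFS, the SAP leaves the population open and the sign can reverse.

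Finally, all sizes rest on assumed medians, transplant shares and timing. That is correct; they show plausible magnitude and are not estimates for this trial.

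**Conclusion.** For OS the concern holds: censoring at SCT is informative because SCT follows response, and the 12.3 curve is likely to understate survival even with no SCT effect. In the main illustration 12-month OS reads 21.5% against a true 31%. This requires that responders live longer than non-responders and are transplanted more often; both are plausible, and neither is quantified in the documents.

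For RFS the same applies only if non-responders are included and their death hazard exceeds the responders' relapse-or-death hazard. For EFS as the SAP defines it, censoring may be informative through selection among responders, but the direction is unknown.

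The consequence is limited to how the additional curves are read. The primary endpoint and the main survival analyses are unaffected. It would be good to change, but it is not essential.

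**What to change.** - Keep the uncensored 12.2 curves as the reported survival estimates, as the SAP already does.
- In 12.3, for OS, fit a Cox model with SCT as a time-dependent covariate and response (CR/CRi, entered from its date) also in the model, or fit SCT as time-dependent among responders only, with time from CR/CRi. Do not rely on Simon-Makuch curves or an unadjusted time-dependent model, which carry the same selection.
- For RFS and EFS, report the cumulative incidence of relapse or death before SCT, with SCT as a competing event. State that this describes what happens before SCT and not what would have happened had SCT not been given.
- State whether RFS includes patients who never reach CR/CRi.
- Label any SCT-censored curve that is kept as hypothetical and resting on independent censoring.

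The cost is a little more programming; the 12.3 rule already requires SCT dates. With 40 patients the model estimates will be imprecise and should be presented as descriptive.

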13.1 Adverse events

All adverse events occurring during the course of the trial and for up to 30 days after the last dose of study medication will be captured, documented and reported. The number of patients developing adverse experiences will be tabulated using [NCI CTCAE] Version 4.03. The CTC v4.03 will be the basis for grading the laboratory changes. Additionally, the subset of adverse experiences considered treatment-related will be summarized. Listings of adverse experiences leading to treatment discontinuation will be provided.

Clinical adverse events and laboratory adverse events will be reported in separate tables. The adverse events will be reported as a whole and additionally based on the severity grading (separate table for grade 3-5 AEs).

Adverse events classified as serious adverse events (SAEs) will be listed separately. Deaths together with the reason for death and the possible relation to study treatment will be summarized.

13.2 Laboratory safety variables

Descriptive statistics of laboratory safety variables (hematology, clinical chemistry, urine analysis, coagulation tests) will be computed, together with the changes from baseline values. The changes from baseline will be analyzed by ANOVA method if feasible.

13.3 Other safety variables

Vital signs (blood pressure, heart rate, temperature) will be summarized with descriptive statistics by visit and dosing group. In addition, the changes from baseline values will be given. The changes from baseline will be analyzed by ANOVA method if feasible. Physical examination, ECG and ECOG results will be summarized with frequency tables.

14 Completion and premature discontinuation

Completion and premature discontinuation will be listed. The reasons for premature discontinuation will be presented.

15 Deviations from the analyses planned in the study protocol

The primary hypothesis of the study was clarified in the Statistical Analysis Plan compared to the definition in the protocol.

16 Execution of statistical analyses

Statistical analyses will be performed by 4Pharma Ltd.

17 Hardware and software

Statistical analysis, tables and patient data listings will be performed with SAS[®] version 9.3 for Windows (SAS Institute Inc., Cary, NC, USA).

18 References

Clinical Study Protocol, Final Protocol, Version 2 (25.08.2015)

19 Appendices

19.1 Schedule of assessments

Assessments by visit	Screening	Baseline	Induction cycle(s)		Consolidation	Maintenance	End of treatment	Follow-up
Time window	Within 14 days prior registration	Before Day 1 of induction	During treatment, twice weekly	End of cycles	Weekly (D2,8, 15,21 ± 2 days)	Twice per cycle (D1,15 ± 2 days)	30 days after last dose/prior to SCT	Every 3 months ± 28 days
Informed consent ¹	X							
Inclusion/exclusion criteria	X							
Demographics	X							
Medical History ²	X							
Pregnancy test ³	X							
Physical examination and ECOG ⁴	X		X	X	X	X	X	
Body height and weight ⁵	X			X	X	X	X	
BSA	X							
Vital signs ⁶	X		X	X	X	X	X	
Standard clinical neurological examination	X							
12-lead ECG	X			X	X	X		
Cardiac ultrasound ⁷	X			X			X	
Hematology ⁸	X		X	X	X	X	X	X
Calculation of GFR ⁹	X			X	X		X	

Clinical chemistry ¹⁰	X			X	X	X	X	
Assessments by visit	Screening	Baseline	Induction cycle(s)		Consolidation	Maintenance	End of treatment	Follow-up
Urine analysis ¹¹	X			X	X	X		
Coagulation test ¹²	X		X	X	X	X		
HIV testing ¹³	X							
Assessment of signs and symptoms, AE	X		X	X	X		X	
CTCAE v 4.03 scale toxicity			X	X	X	X	X	
Concomitant medication	X		X	X	X	X	X	
Bone Marrow Aspirate ¹⁴	X			X	X	X		X
Survival								X
Selinexor baseline dose ¹⁵		X						
Bone marrow aspirates for translational research ¹⁶ (optional)		X						
Blood draws for translational research ¹⁷ (optional)			X		X			
Blood draws for Pharmacokinetics ¹⁸ (optional)			X					
Ophthalmological examination ²⁰	X							

Notes¹ Prior to the first study-specific measures² Medical history includes baseline symptoms as well as a detailed history of prior cancer therapies including start and stop dates, disease progression during or after therapy, as well as discontinuations due to intolerance or any other serious illness.

³ Applicable for women of childbearing potential. Serum β -HCG test within 7 days before the first dose of study drug. To be repeated by urine test, if date of first result exceeds the 7-day window

⁴ Full physical examination for baseline and end of study visit. Physical examinations during the study should be symptom directed.

⁵ Body height will be measured at screening only.

⁶ Vital signs: blood pressure, pulse and temperature

⁷ Echocardiography of left ventricular ejection fraction (LVEF) to observe cardiac toxic city of idarubicin. at baseline, before a second facultative induction course and before first consolidation therapy. Maybe repeated if clinically indicated.

⁸ Hematology: hemoglobin, red blood cell (RBC) count, platelets, white blood cell (WBC) count and WBC differential (neutrophils, lymphocytes), leukemic blasts.

⁹ Calculated GFR according to the formula of Cockcroft and Gault.

¹⁰ Clinical chemistry: Sodium, Potassium, Calcium, Creatinine, Total Bilirubin, Alkaline Phosphatase, alanine aminotransferase (ALT), aspartate aminotransferase (AST), Total Protein, Albumin, LDH

¹¹ Urine analysis will include urine bilirubin, glucose, hemoglobin, ketones, pH, protein (once per cycle in consolidation/maintenance)

¹² Coagulation test include prothrombin time (PT) and activated partial thromboplastin time (aPTT) (once per cycle in consolidation/maintenance)

¹³ If not performed within the last 6 months

¹⁴ Including cytogenetic, flow cytometry and molecular analysis (FLT3 ITD or TKD mutation or NPM-1 mutation, FLT3 ITD at baseline only) at baseline, end of each induction and consolidation cycle. In maintenance and FU after SCT if blood count is suspicious for progression of disease/relapse.

¹⁵ Baseline Selinexor dosing: single dose given after registration but before beginning of first induction cycle.

¹⁶ Bone marrow aspirates for translational research will be taken prior to baseline Selinexor dose and 24 hour post-baseline dose. 2 ml of each aspirate will be used to isolate viable cells for mouse studies; 2 ml of each aspirate will be processed to isolate RNA for stem cell expression array analysis.

¹⁷ Blood draws for translational research (exploratory pharmacodynamic analysis): (2 x 2.5 ml for XPO1 inhibition in leukocytes, 2 ml for cytokines) will be collected on day of first in-clinic dose of Selinexor during each induction and consolidation cycle. 2 x 2.5 ml, plus 2 ml blood will be collected pre-dose and 2 x 2.5 ml will be collected 4 hr post-dose.

¹⁸ Blood draws (2 ml) for PK analysis will be performed during first induction cycle on day of first in-clinic dose of Selinexor: pre-dose, 2 hr and 4 hr post-dose.

¹⁹ Follow-up is to include all patients, including those having undergone SCT

²⁰ required at screening and if clinically indicated during the treatment phase. Ophthalmologic examination includes:

- prior to dilation: best corrected visual acuity and slit lamp examination including tonometry
- following dilation: fundoscopy and a slit lamp exam to document lens clarity.

